6.3.1 Neurological Toxicity

The most common neurotoxicity related to fludarabine or cytarabine administration is an acute cerebellar syndrome that may manifest itself as ataxia, nystagmus, or dysarthria. However, seizures and encephalopathy have also occurred following therapy with high dose cytarabine. Patients experiencing Grade 3 or 4 cerebellar toxicity should be removed from protocol therapy.

6.3.2 Ara-C Syndrome including Fever, Rash, or Conjunctivitis

Do not withhold cytarabine for fever if it is likely to have been caused by the cytarabine. However, blood cultures should be obtained even if fever is thought to be likely due to cytarabine. Institution of antibiotics for fever associated with cytarabine infusion is at the discretion of the treating physician (see fever management recommendations in the COG Supportive Care Guidelines).

For rash or conjunctivitis, withhold cytarabine for Grade 3-4 toxicity until resolved to \leq Grade 1. Make up missed doses and consider concurrent treatment with hydrocortisone or dexamethasone, and/or with dexamethasone ophthalmic drops for conjunctivitis only.

6.3.3 Renal Toxicity

6.3.3.1 Cytarabine

Patients with nephrotoxicity secondary to antibiotics, or antifungals, may have prolonged excretion of cytarabine leading to more severe marrow and extramedullary toxicity.

- Patients with a serum creatinine > 2 mg/dL or $> 2x$ normal for age should be hydrated orally or intravenously. Following hydration, the patient must have a creatinine clearance ≥ 60 mL/min/1.73m² as measured preferably by a nuclear GFR scan, timed urine collection for

creatinine clearance, or calculated by the Schwartz formula before proceeding with cytarabine therapy.

- If the creatinine clearance is abnormal ($< 60 \text{ mL/min}/1.73\text{m}^2$) then Cycle 2 high dose cytarabine should be reduced by 50% for each daily dose. With this approach, previous research has shown the prevention of subsequent neurotoxicity in recipients of high dose cytarabine in the face of renal insufficiency.²⁵

6.3.3.2 **Fludarabine**

Renal clearance accounts for about 40% of the total body clearance of fludarabine and clearance of the primary active metabolite is decreased in patients with renal impairment. Renal elimination appears to become more important at high dosages of the drug. The dose of fludarabine needs to be adjusted in patients with moderate renal impairment. The following are suggested guidelines for dose adjustment of fludarabine in renal impairment:

GFR $> 50 \text{ mL/minute}/1.73\text{m}^2$: no adjustment required
GFR 30-50 mL/minute/1.73m²: administer 80% of the dose
GFR $< 30 \text{ mL/minute}/1.73\text{m}^2$: not recommended
Hemodialysis: administer 25% of the dose

Continuous ambulatory peritoneal dialysis (CAPD): not recommended

Continuous renal replacement therapy (CRRT): Administer 80% of dose²⁶

6.3.4 **Hand-Foot Syndrome**

Hand-foot syndrome has been reported in patients treated with high-dose cytarabine. Patients who develop hand-foot syndrome may receive topical emollients (such as Aquaphor) as well as topical or systemic steroids or antihistamines if appropriate. Oral administration of vitamin B6 (pyridoxine) can also be used for these patients- BSA $< 0.5 \text{ m}^2$: 50 mg per day; BSA 0.5-1.0 m²: 100 mg per day; BSA 1.1-1.5 m²: 200 mg per day, and BSA $> 1.5 \text{ m}^2$: 300 mg per day.

6.3.5 **MLN4924 (pevonedistat) dose modification for hepatic toxicity:**

AST, ALT, and bilirubin should be checked and read prior to each dose of MLN4924 (pevonedistat) and then weekly.

If a patient experiences \geq Grade 3 elevation of ALT/AST/bilirubin that does not return to \leq Grade 1 or baseline prior to the next dose of MLN4924 (pevonedistat), the dose will be held and this will be considered a DLT. However, patients can still receive azacitidine as scheduled and can receive subsequent fludarabine and cytarabine if ALT \geq Grade 3 after discussion with study chair. NOTE: See [Appendix III](#) for values that represent thresholds between CTCAE grades.

Patients who experience a dose limiting toxicity during cycle 1 that resolves to baseline or \leq Grade 1 at the time of next cycle can proceed with the next cycle at dose level -1.

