6.2 Dose Modifications for Non-Hematological Toxicity

6.2.1 Patients will have ALT/AST/bilirubin evaluated prior to each planned dose of MLN4924 (pevonedistat) in order to determine whether the scheduled dose

should be administered. It is anticipated that ALT and AST may be elevated for approximately 48 hours following the end of the 1st MLN4924 (pevonedistat) infusion.

NOTE: See [Appendix III](#) for toxicity grading table.

If a patient experiences > Grade 3 elevation of ALT/AST on or after Cycle 1, Day 1 then the Cycle 1, Day 3 MLN4924 (pevonedistat) dose should not be given. If ALT/AST returns to \leq Grade 1 or baseline values by Day 5 then the patient should receive their Day 5 MLN4924 (pevonedistat) dose and this will not be considered a DLT. If ALT/AST does not return to \leq Grade 1 or baseline values by Day 5 then MLN4924 (pevonedistat) should be held and this will be considered a DLT. Persistent elevations of ALT/AST > Grade 2 beyond 2 days between any other doses after Cycle 1, Day 1 will be considered a DLT.

6.2.2 Patients who experience a dose limiting toxicity during cycle 1 that resolves to baseline or < Grade 1 at the time of next cycle can proceed with the next cycle at dose level -1.

6.3 **Modifications and Supportive Care Recommendations for Toxicity Related to Protocol Therapy (Cycle 1 and Cycle 2)**

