11.2 Definitions

11.2.1 Evaluable For Adverse Events

Any patient who receives at least 2/3 doses of MLN4924 (pevonodistat) during Cycle 1 or who experiences a dose-limiting toxicity is considered evaluable for Adverse Events. In addition, for the dose-confirmation portion during Cycle 1, patients must receive at least 85% of the prescribed dose per protocol guidelines and must have the appropriate toxicity monitoring studies performed to be considered evaluable for dose limiting toxicity. Patients who do not have DLT and are not considered evaluable for toxicity will be replaced.

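### Section 6.3.3.1 contradicts itself for Cycle 2 patients with raised serum creatinine whose clearance stays below 60 after hydration: one bullet holds cytarabine, the next gives half of each daily dose

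*Combined protocol and SAP*

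**What the plan says.** Section 6.3.3.1 of the protocol governs cytarabine in patients with renal impairment. It opens by warning that kidney damage from antibiotics or antifungals can slow cytarabine excretion and worsen marrow and extramedullary toxicity. Two bullets follow.

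- **First bullet.** A patient whose serum creatinine exceeds 2 mg/dL, or twice what is "normal for age should be hydrated orally or intravenously". Then: "Following hydration, the patient must have a creatinine clearance" of at least 60 mL/min/1.73 m² "before proceeding with cytarabine therapy". No cycle is named and no exception is given.
- **Second bullet.** "If the creatinine clearance is abnormal", meaning below 60 mL/min/1.73 m², "then Cycle 2 high dose cytarabine should be reduced by 50% for each daily dose". No serum creatinine condition is attached. The sentence after it cites earlier research in which this approach prevented neurotoxicity in patients with renal insufficiency.

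The heading of Section 6.3, under which both bullets sit, names both Cycle 1 and Cycle 2.

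**The concern.** For one group of patients the two bullets cannot both be followed. In Cycle 2, a patient who meets the creatinine trigger and remains below 60 after hydration may not proceed with cytarabine under the first bullet, yet receives it at half of each daily dose under the second.

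The protocol itself says why this matters: it links renal impairment to more severe cytarabine toxicity and to neurotoxicity. Two sites could read the same laboratory result and act differently, and both could claim to have followed the protocol. Cycle 2 toxicity belongs to the descriptive summary of all toxicities in Section 11.3, and response is a secondary aim (Section 1.2). Both descriptions would then mix patients managed under different rules for the same finding.

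**Working it through.** No sample size, error rate or other statistical figure is involved, so the check is a case-by-case reading of the two bullets.

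**Inputs**

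- Trigger, first bullet: serum creatinine above 2 mg/dL or above twice normal for age (6.3.3.1).
- Requirement, first bullet: clearance of at least 60 mL/min/1.73 m² after hydration; any cycle (6.3.3.1, under the 6.3 heading).
- Trigger, second bullet: clearance below 60; action: Cycle 2 cytarabine halved (6.3.3.1).
- Planned cytarabine: five daily doses on Days 6-10, each 2000 mg/m² from age 1 year and 67 mg/kg below 1 year (5.2).

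**All combinations** (2 trigger states × 2 clearance bands × 2 cycles = 8)

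| Creatinine trigger | Clearance | Cycle | First bullet | Second bullet | Result |
|---|---|---|---|---|---|
| Met | ≥ 60 | 1 | Proceed | Not engaged | Consistent |
| Met | ≥ 60 | 2 | Proceed | Not engaged | Consistent |
| Met | < 60 | 1 | Hold | Silent | One instruction |
| **Met** | **< 60** | **2** | **Hold** | **Give half of each dose** | **Contradiction** |
| Not met | ≥ 60 | 1 | Not engaged | Not engaged | Consistent |
| Not met | ≥ 60 | 2 | Not engaged | Not engaged | Consistent |
| Not met | < 60 | 1 | Not engaged | Silent | **No instruction** |
| Not met | < 60 | 2 | Not engaged | Give half of each dose | One instruction |

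One combination has two incompatible instructions, one has none where one is needed, and six are clear.

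**What each bullet implies for the contradicted group**

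- First bullet: no cytarabine while clearance stays below 60. If it recovers to 60 or more, the patient may proceed, and the bullet attaches no reduction.
- Second bullet: 0.5 × 2000 = 1000 mg/m² per dose, or 5 × 1000 = 5000 mg/m² over the course against a planned 5 × 2000 = 10,000 mg/m². Below 1 year of age: 0.5 × 67 = 33.5 mg/kg per dose, or 5 × 33.5 = 167.5 mg/kg against 5 × 67 = 335 mg/kg.

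**Does another section decide between them?**

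- Section 5.2 (treatment details): the cytarabine entry has no renal rule.
- Section 5.3 (starting Cycle 2): names bilirubin, ALT, AST and recovery of toxicities related to pevonedistat. It has no clearance criterion, so renal impairment caused by an antibiotic would not by itself stop a patient from reaching Cycle 2.
- Section 6.1 (hematological toxicity): leaves the cytarabine dose unchanged and does not address renal function.

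None says which bullet governs.

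**The case against.** The strongest reply is that the text can be read coherently: the first bullet is a general step to hydrate and recheck, and the second is the specific rule for Cycle 2 when clearance stays abnormal. The sentence on neurotoxicity lends this some support, because it describes the reduction as an approach for patients who do have renal insufficiency. A second harmonizing reading confines the second bullet to patients below 60 who never met the creatinine trigger.

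Both readings are possible, but the protocol states neither, and they give opposite answers for the contradicted group: half of each dose under one, a hold under the other. The second is also the less natural, since the clearance that the second bullet calls abnormal reads most easily as the one just measured under the first.

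The reply is right about the limits of the consequence. The DLT observation period is the first cycle (Section 5.6), so the contradiction cannot alter the MTD or RP2D decision. Response is reported descriptively (Section 11.5) in a study without a comparator arm. Section 6.0 requires the Study Chair to be told of any dosage modification, which may limit divergence between sites but does not settle the wording. Entry requires adequate renal function (Section 4.1.5.1), so the group may be small.

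A reader might also infer that a renal hold in Cycle 1 costs a patient DLT evaluability, because "patients must receive at least 85% of the prescribed dose per protocol guidelines" (Section 11.2.1). The documents do not support that as part of this point. The second bullet is silent in Cycle 1, so there is no contradiction there. The 85% rule does not name a drug. If it covers cytarabine, omitting one of five doses leaves 4/5 = 80%, below the threshold. If it means pevonedistat only, that drug's last dose is on Day 5, before cytarabine starts on Day 6, and the hold has no effect. The rule's reference to protocol guidelines might also excuse a hold that the protocol itself directs.

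**Conclusion.** The contradiction is real and should be corrected. It is an internal inconsistency in clinical-management wording, and it is narrow: Cycle 2, creatinine trigger met, clearance below 60 after hydration. For that group the plan calls both for a hold until recovery and for 50% of each daily cytarabine dose. A separate gap exists in Cycle 1, where clearance below 60 without the creatinine trigger has no instruction.

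Two broader inferences do not hold. The conflict does not reach every patient with clearance below 60, because the first bullet applies only after the creatinine trigger. Nor is the contrast simply none against half: the first bullet sets a condition to be met, so cytarabine is omitted altogether only if clearance never recovers.

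The conclusion rests on reading the first bullet as applying in both cycles, which its text and the Section 6.3 heading support. What is at stake is patient safety and a uniform description of Cycle 2 toxicity and response, not the Cycle 1 dose decision. How many patients would be affected cannot be estimated from the documents.

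**What to change.** The sponsor should reconcile the two bullets of Section 6.3.3.1 so that each combination of creatinine trigger, clearance band and cycle carries exactly one instruction. A short table laid out like the one above would do it. In particular, the amended text should:

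1. say which instruction governs in Cycle 2 when the creatinine trigger is met and clearance remains below 60 after hydration;
2. state the cycle or cycles and the patients to which each bullet applies;
3. supply an instruction for Cycle 1 when clearance is below 60 and the creatinine trigger is not met.

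Which clinical rule to adopt in each case is the sponsor's decision, and no view is taken here. The cost is a wording amendment; sample size, dose-finding rules and planned analyses are untouched.

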5.0 TREATMENT PROGRAM

5.1 Overview of Treatment Plan

The primary purpose of this feasibility study is to evaluate the safety and toxicity profile of MLN4924 (pevoneditstat) in combination with azacitidine, fludarabine, and cytarabine in children with relapsed or refractory AML or MDS and to recommend a phase 2 dose for use in further studies. A rolling 6 design will be utilized. Patients will receive 1 dose of intrathecal cytarabine with a diagnostic lumbar puncture to be performed prior to the start of each cycle of therapy.

For patients ≥ 1 year of age, MLN4924 (pevoneditstat) will be administered at 20 mg/m²/dose intravenously (IV) on days 1, 3 and 5. Azacitidine will be administered at 75 mg/m²/dose IV once daily on days 1-5. On days 1, 3, and 5 when both drugs are administered, azacitidine will be administered first followed by MLN4924 (pevoneditstat) infusion. The infusion of MLN4924 (pevoneditstat) will begin between 30-60 minutes after completion of IV azacitidine. Following completion of azacitidine and MLN4924 (pevoneditstat), fludarabine 30 mg/m²/dose IV once daily and cytarabine 2000 mg/m²/dose IV once daily will be administered on days 6-10. Cytarabine infusion will begin 4 hours after the start of fludarabine.

For patients < 1 year of age, MLN4924 (pevoneditstat) will be administered at 15 mg/m²/dose intravenously (IV) on days 1, 3, and 5. Azacitidine will be administered at 2.5 mg/kg/dose IV once daily on days 1-5. On days 1, 3, and 5 when both drugs are administered, azacitidine will be administered first followed by MLN4924 (pevoneditstat) infusion. The infusion of MLN4924 (pevoneditstat) will begin between 30-60 minutes after completion of IV azacitidine. Following completion of azacitidine and MLN4924 (pevoneditstat), fludarabine 1 mg/kg/dose IV once daily and cytarabine 67 mg/kg/dose IV once daily will be administered on days 6-10. Cytarabine infusion will begin 4 hours after the start of fludarabine.

Patients without additional evidence of CNS disease (CNS1) do not require additional CNS-directed therapy during the cycles. Patients with blasts detected in the CNS (CNS2/3) will receive additional intrathecal chemotherapy with IT cytarabine or IT triple therapy (cytarabine, hydrocortisone, methotrexate) per institutional standards at a schedule of 2x/weekly until the CNS is clear of blasts on 2 consecutive LPs, with a minimum of 4 IT cytarabine or IT triple (ITT) doses administered.

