5.4.2 Intra-Patient Escalation

Intra-patient dose escalation is not allowed.

5.5 **Grading of Adverse Events**

Adverse events (toxicities) will be graded according to the NCI Common Terminology Criteria for Adverse Events (CTCAE) version 5.0. All appropriate treatment areas should have access to a copy of the CTCAE version 5.0. A copy of the CTCAE version 5.0 can be downloaded from the CTEP website (http://ctep.cancer.gov/protocolDevelopment/electronic_applications/ctc.htm). Any suspected or confirmed dose-limiting toxicity should be reported immediately (within 24 hours) to the Study Chair.

5.6 **Definition of Dose-Limiting Toxicity (DLT)**

DLT will be defined as any of the following events that are possibly, probably or definitely attributable to protocol therapy. The DLT observation period for the purposes of dose-confirmation will be the first cycle of therapy.

Dose limiting hematological and non-hematological toxicities are defined differently.

5.6.1 Non-hematological dose-limiting toxicity:

5.6.1.1 All Grade 3 or greater non-hematological toxicity not clearly related to the underlying disease and attributable to protocol therapy will be considered a DLT except:

- Grade 3 or 4 elevation of ALT/AST that returns to Grade ≤ 1 within 14 days. NOTE: For the purposes of this study the ULN for ALT is defined as 45 U/L regardless of baseline and for AST is defined as 50 U/L regardless of baseline. See [Appendix III](#) for values that represent thresholds between CTCAE grades.

THIS PROTOCOL IS FOR RESEARCH PURPOSES ONLY, SEE PAGE 1 FOR USAGE POLICY

- Grade 3 or 4 electrolyte abnormalities that resolve, with or without supplementation intervention, to \leq Grade 2 within 72 hours. Electrolyte supplementation is encouraged.
- Grade 3 arthralgia/myalgia that returns to Grade \leq 2 within 5 days on analgesics
- Grade 3 or 4 fever, febrile neutropenia, or infection with or without hospitalization
- Grade 3 tumor lysis syndrome
- Alopecia
- Grade 3 maculo-papular or morbilliform rash that resolves to \leq Grade 2 within 7 days
- Grade 3 mucositis that resolves (with or without supportive care) to \leq Grade 2 within 14 days
- Grade 3 fatigue or anorexia responsive to supportive care within 7 days
- Grade 3 nausea, vomiting, and/or diarrhea responsive to supportive care within 72 hours
- Early intervention with TPN or enteral tube feeding for anorexia, nausea, or concern for poor nutritional status

5.6.2 Hematological dose-limiting toxicity:

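### In Cycle 1 no liver test is required between the third pevonedistat dose (Day 5) and the Days 8 to 14 weekly test, although fludarabine and high-dose cytarabine start on Day 6

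*Combined protocol and SAP*

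**What the plan says.** - **Test schedule.** Section 6.3.5 says that "AST, ALT, and bilirubin should be checked and read prior to each dose of MLN4924", and then weekly. The Section 8.1 table with footnote 8 and item p of the Cycle 1 delivery map (Appendix VIII-A) agree. The map lists item p on Days 1, 3 and 5, lists no study on Days 6 and 7, and next shows item p in the block for Days 8 to 14.
- **Purpose and expected rise.** Section 6.2.1 uses the pre-dose tests to decide whether the scheduled pevonedistat dose is given. It adds: "It is anticipated that ALT and AST may be elevated for approximately 48 hours following the end of the 1st MLN4924" infusion.
- **Chemotherapy.** Section 5.1 puts fludarabine and cytarabine on Days 6 to 10. "Cytarabine infusion will begin 4 hours after the start of fludarabine".
- **Hepatic rule.** Under Section 6.3.5, if a Grade 3 or higher ALT, AST or bilirubin has not come down to Grade 1 or baseline "prior to the next dose of MLN4924 (pevonedistat), the dose will be held and this will be considered a DLT". It then says that "patients can still receive azacitidine as scheduled and can receive subsequent fludarabine and cytarabine if ALT" is Grade 3 or higher, after discussion with the study chair.
- **DLT.** Section 5.6 counts "any of the following events that are possibly, probably or definitely attributable to protocol therapy". Section 5.6.1.1 exempts a "Grade 3 or 4 elevation of ALT/AST that returns to Grade" 1 or lower within 14 days.
- **Latitude.** Appendix VIII-A tells sites to obtain other studies as good care requires, and Section 7.3 strongly recommends hospitalization after each cycle of chemotherapy.

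**The concern.** The tests are tied to the next pevonedistat dose, and dose 3 has no next dose in the cycle. It is therefore the only dose without a required test about two days later, and the one followed most closely by fludarabine and high-dose cytarabine.

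Two things are at stake. First, primary aim 1.1.2 is to define and describe the toxicities, and the pevonedistat risk list (Section 9.1.10) gives ALT and AST increases as likely (>20%). A short rise after dose 3 may not appear in the required data. Second, the last required value before Day 6 was drawn before dose 3. A rise caused by dose 3 therefore cannot prompt the study chair discussion from required data. A first abnormal value on Day 8 or later is also harder to attribute to one drug, because Section 9.3.2 lists hepatotoxicity for cytarabine.

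**Working it through.** **Timing.** Inputs: azacitidine over 15 minutes, a gap of 30 to 60 minutes, and pevonedistat over 60 minutes (Section 5.2). Assumption: pre-dose and weekly draws are taken at the clock time at which azacitidine starts.

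Infusion end = 0.25 + (0.5 to 1) + 1 = 1.75 to 2.25 h after azacitidine starts.

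| Interval from infusion end | Calculation | Result |
|---|---|---|
| Doses 1 and 2 to the next pre-dose test | 48 − (1.75 to 2.25) | 45.75 to 46.25 h |
| Dose 3 to fludarabine on Day 6 (same clock time) | 24 − (1.75 to 2.25) | 21.75 to 22.25 h |
| Dose 3 to a Day 8 test | 72 − (1.75 to 2.25) | 69.75 to 70.25 h |
| Dose 3 to a Day 12 test (weekly counted from Day 5) | 168 − (1.75 to 2.25) | 165.75 to 166.25 h |

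If a rise after dose 3 also lasted 48 h, it would be over 21.75 to 22.25 h before a Day 8 test. By then two of the five fludarabine/cytarabine days have been given.

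**Effect on the 14-day rule.** Take a Grade 3 or 4 ALT/AST elevation with onset on day O, lasting D whole days. Observed duration = (first test at or after day O + D) − (first abnormal test). It counts as a DLT if the observed duration exceeds 14 days, and it truly is one if D exceeds 14.

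Present calendar, tests on Days 8, 15, 22 and 29, O = 6:

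- D = 1 or 2: recovered by Day 8, so unseen.
- D = 15 or 16: recovery on Day 21 or 22, seen on Day 22; 22 − 8 = 14, so wrongly exempt.
- D = 17: recovery on Day 23, seen on Day 29; 29 − 8 = 21, so correctly a DLT.

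If a site's first test is Day 12 or Day 14 and weekly after that, unseen durations become 1 to 6 or 1 to 8 days, and wrongly exempted durations 15 to 20 or 15 to 22 days. These readings are less natural than Day 8, but the text does not exclude them.

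**Testing the remedy, O = 6.**

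- Add a Day 6 draw to the weekly tests only. For D = 10 to 14 (recovery on Days 16 to 20) recovery is first seen on Day 22; 22 − 6 = 16, so five durations become false DLTs.
- Add twice-weekly repeats. False DLTs remain at D = 13 to 14 (extra draws on Days 11, 18, 25) or D = 14 (extra draws on Days 12, 19, 26).
- Add a draw 14 days after the first such value, Day 20. D = 13 or 14 is seen as recovered at 20 − 6 = 14. No false DLT remains.

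**Onset on Day 7, after the Day 6 draw.** The first abnormal test is Day 8 with or without the remedy. One day is unseen and D = 15 is misclassified, as in the present Day 8 calendar.

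**Context.** In the adult azacitidine combination trial (Section 2.3.1), 2 of 55 patients at 20 mg/m² had a DLT: 2/55 = 3.6% (Clopper-Pearson 95% interval 0.4% to 12.5%). Both were transient transaminase elevations. No frequency for rises after dose 3 can be taken from this.

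**The case against.** The best defence is that the pre-dose tests are dosing gates, as Section 6.2.1 says, and no gate is needed after the last dose. The 48 h figure is given for the first infusion only, so carrying it to dose 3 is an inference. The study chair sentence follows the held-dose rule and may be meant mainly for patients whose abnormal Day 3 or Day 5 value is already known. It leads at most to a discussion, since Section 6.3 gives no hepatic hold or reduction for fludarabine or cytarabine. Drug-level confounding matters little for DLT counts, because Section 5.6 attributes events to protocol therapy as a whole. Most rises that would be missed are short ones that the plan deliberately exempts. Only the most severe grade per cycle is reported (Sections 13.4.1 and 13.4.2), so data are lost only when the rise after dose 3 is the patient's first or highest.

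The remedy is also imperfect. A Day 6 draw at about 22 to 24 h does not reproduce the 46 h check after doses 1 and 2. A Day 7 draw would, but only after fludarabine and cytarabine have begun.

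All of this stands and limits the point. It does not supply a required value after dose 3 and before chemotherapy. A Day 5 pre-dose value about one day old, probable inpatient care and freedom to test more often lessen the gap, but leave capture to each site.

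**Conclusion.** The gap is real, and closing it is a cheap improvement; the schedule is not wrong as written. Required testing leaves at least about 70 h after dose 3 uncovered, against about 46 h after doses 1 and 2. The cost falls on toxicity description and on the input to the study chair discussion.

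Three stronger readings are tempting and are not supported:

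- *A rise after dose 3 goes undetected.* The documents show only that no test is required; sites may draw one.
- *The DLT count or the recommended dose is at risk.* With a Day 8 test and onset on Day 6, misclassification is confined to elevations of 15 to 16 days, and the 14-day rule still applies after dose 3.
- *The plan breaks its own rule of testing within 48 h of each dose.* It states no such rule.

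The sizes rest on a constant clock time, whole-day durations, a chosen onset day and the 14 days being counted from the first abnormal test. They carry no probabilities.

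**What to change.** For Cycle 1, in Sections 8.1 and 6.3.5 and Appendix VIII-A:

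1. Require ALT, AST and bilirubin on Day 6, read before fludarabine. If the sample is shared with the 24-hour PK draw after the Day 5 dose (Section 8.2.2, both weight groups), have it read before cytarabine. Use the value for the existing study chair discussion.
2. Name Day 8 for the first weekly test, then Days 15, 22 and 29. Onset on Day 7 is caught only by this test.
3. Repeat any Grade 3 or higher value with the twice-weekly CBC draws until Grade 1 or less, including one draw 14 days after the first such value. Items 1 and 3 must be adopted together, because item 1 alone creates false DLTs.

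**Cost.** One extra chemistry and a small blood volume. If fludarabine starts at azacitidine's clock time, the PK draw falls 1.75 to 2.25 h after fludarabine starts and, since cytarabine starts at 4 h, 1.75 to 2.25 h before cytarabine. Sharing it needs no extra draw but gives a pre-cytarabine value only. A pre-fludarabine value needs a separate draw or fludarabine about 2 h later. Naming Day 8 adds no test. Repeats affect only patients with a Grade 3 or higher value and add at most one separate draw. More transient elevations will be recorded.
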